6.2 MEASURES TO MINIMIZE BIAS: RANDOMIZATION AND BLINDING

Eligible participants will be randomized into either the intervention group or the control group. In order to provide more opportunities for participants to accept EAW training, the intervention group will have 20 participants, and the control group will have 10 participants.

7 STUDY INTERVENTION DISCONTINUATION AND PARTICIPANT DISCONTINUATION/WITHDRAWAL

7.1 DISCONTINUATION OF STUDY INTERVENTION

Subjects may be withdrawn without their consent if it is found that they do not meet eligibility criteria for the study, or if during an exoskeleton instruction session, research staff or clinicians have concerns about the participant's performance or safety and feel that discontinuing involvement would be in the best interest of the participant.

7.2 PARTICIPANT DISCONTINUATION/WITHDRAWAL FROM THE STUDY

If subjects decide to stop being in the research study, they can contact the Principal Investigator or the research staff. There are no early withdrawal procedures that will be required of participants.

Participants may also withdraw their permission for the use and disclosure of any of their protected information for research, but they must do so in writing to the Principal Investigator at the address on the first page. Even if they withdraw their permission, the Principal Investigator for the research study may still use the information that was already collected if that information is necessary to complete the research study. Their health information may still be used or shared after their withdraw their authorization if they have an adverse event from participating in the research study.

If they decide they don't want their samples and/or data to be used for research anymore, they can contact the researcher and ask to have their samples and/or data removed from future use. If any samples or data have already been shared without their identity, it won't be possible to retrieve them because no one will know who they are.

Samples and data that have already been used will not be affected by their decision. Any samples and/or data that are still linked to their identity by a code the researcher has will be withdrawn so that no future sharing of their samples and/or data will take place. If their samples have already been deposited in an external repository, the study team will request that their samples be removed.

7.3 LOST TO FOLLOW-UP

N/A

8 STUDY ASSESSMENTS AND PROCEDURES

8.1 EFFICACY ASSESSMENTS

Demographic data:

1. Age: age of patient in years
2. Sex: male (M) or female (F)
3. Race: race of patient
4. Diagnosis: primary diagnosis of the patient from medical chart (include level of injury from the International Standard for Neurological Classification of Spinal Cord Injury (ISNCSCI) examination and the completeness of injury from American Spinal Injury Association Impairment Scale (AIS)) at admission and discharge.
5. Date (or year) of injury: the date of getting the diagnosis
6. Admission date: the date that the patient starts acute inpatient rehabilitation
7. Discharge date: the date that the patient discharged

Pain scale: 1) International Spinal Cord Injury Basic Pain Data Set (ISCIBPDS) to identify pain locations, average intensity (over the past three days), and influence on daily activities. 2) Spinal Cord Injury Pain Instrument (SCIPI) to classify patients' neuropathic or nociceptive pain. ISCIBPDS and SCIPI will be performed on the enrollment and discharge dates. 3) Participants' current level of pain before and after walking training will be recorded in the walking session data form.

Walking session results include session date, total up time, total walk time, and total steps. If subjects can walk independently 10-meter walking test and Walking Index for Spinal Cord Injury II (WISCI II) will be tested. In the 10 MWT, the participant will be asked to walk 10 meters (without the exoskeleton) at their fastest, comfortable pace. The time to cover this distance will be timed with a stopwatch. The 20-item WISCI-II provides a rank-order rating of the ability of a person with SCI to walk 10 meters in relation to the severity of impairment. Ratings consider the amount of assistance and the types of assistive devices (e.g., leg braces) required to walk. Both the 10 MWT and WISCI II will be evaluated after enrollment (within 1-2 days) and before discharge from AIR (± 2 days).

The presence and degree of systemic inflammation will be determined by measuring the concentration of serum C-reactive protein (CRP). CRP is an acute-phase protein that rises in response to inflammation. It is not specific to inflammation caused by SCI. Six ml of blood will be drawn in a red top tube, two times (after enrolling into the study and before discharge) for a total of 12 ml of blood over the course of the full study for analyses of the inflammatory markers. CRP is routinely measured from patients clinically when it is important to assess the degree of inflammation is present. The analysis will compare changes in levels of CRP pre- and post-intervention, in both the EAW with AIR or AIR groups.

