5 STUDY POPULATION

5.1 INCLUSION CRITERIA

1. Age 18 years or greater
2. Height between 5'2" and 6'2" (1.6 meters to 1.9 meters)
3. Weight less than 220 pounds (100 kilograms)
4. Near Normal range of motion (ROM), as follows: 1) Hip: more than 5 degrees of extension and 110 degrees of flexion; 2) Knee: Full extension to 110 degrees of flexion; 3) Ankle: at least 0 degree of dorsiflexion to 25 degrees of plantarflexion
5. Are eligible for locomotor training as part of inpatient rehabilitation
6. Independent with static sitting balance
7. Sufficient function upper extremity strength to manage walking aid (front-wheeled walker, platform walker, or crutches)
8. Able to follow directions

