9.2 STATISTICAL ANALYSES

9.2.1 GENERAL APPROACH

All statistical tests will be 2-sided. The outcome measures will be tested at a 0.05 level of significance. SPSS will be used to conduct the statistical analyses. All participants who have EAW sessions will be included (regardless of the number of sessions they complete before discharge, but the number and reason of missing EAW sessions will be recorded). To test the three main hypotheses of the proposed study, the change score of each outcome between baseline and discharge will be calculated. The change score will be compared between the intervention and control groups using independent t-test analyses (if the outcomes are not normally distributed, Mann-Whitney tests will be used).

In addition to the primary analysis, several secondary analyses will be performed. 1) Each of the outcomes will be compared between pre- and post-EAW training using a paired t-test analysis (if the outcomes are not normally distributed, Wilcoxon signed-rank test will be used). 2) Analyses will be performed to determine the relationships between the change of outcome measures and EAW training time (including sessions, up time, walking time, or total number of steps per session and across all sessions) using correlation coefficients, regression analyses (stepwise and logistic), analyses of covariance, and nonparametric analyses as appropriate. 3) An additional exploratory post

hoc analyses will be to determine the relationship of participant's baseline characteristics with successful use of the exoskeleton. This post hoc analysis would serve as pilot data to begin to determine who is a good candidate for EAW training during AIR for a future study.

References:

1. Simpson, L.A., et al., *The health and life priorities of individuals with spinal cord injury: a systematic review*. J Neurotrauma, 2012. **29**(8): p. 1548-55.
2. Ditunno, P.L., et al., *Who wants to walk? Preferences for recovery after SCI: a longitudinal and cross-sectional study*. Spinal Cord, 2008. **46**(7): p. 500-6.
3. Tate, D.G., C.Z. Kalpakjian, and M.B. Forchheimer, *Quality of life issues in individuals with spinal cord injury*. Arch Phys Med Rehabil, 2002. **83**(12 Suppl 2): p. S18-25.
4. [name], T.N. and K.T. Ragnarsson, *Pain after spinal cord injury*. Phys Med Rehabil Clin N Am, 2000. **11**(1): p. 157-68.

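### The 10MWT and WISCI II are taken only in independent walkers, with no score for anyone else, so participants who gain walking have no change score on either test

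*Combined protocol and SAP*

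**What the plan says.** Section 8.1 (Efficacy Assessments) makes both walking tests conditional: "If subjects can walk independently 10-meter walking test and Walking Index for Spinal Cord Injury II (WISCI II) will be tested". For the 10MWT, "the participant will be asked to walk 10 meters (without the exoskeleton) at their fastest, comfortable pace". For WISCI II, "Ratings consider the amount of assistance and the types of assistive devices (e.g., leg braces) required to walk". Both tests are planned twice, shortly after enrolment and around discharge. No value, category or missing-data rule is given for a participant who does not meet the condition.

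Section 5.1 does not require walking at entry. It asks for independent static sitting balance, enough arm strength to manage a walking aid, and that participants "Are eligible for locomotor training as part of inpatient rehabilitation".

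Neither test appears among the primary, secondary or tertiary endpoints in section 1.1 or section 3. In section 9.2.1 the comparison between arms opens with "To test the three main hypotheses of the proposed study" and continues: "the change score of each outcome between baseline and discharge will be calculated". The test is an independent t-test, or Mann-Whitney if the outcome is not normally distributed. The same section adds a paired pre/post analysis of each outcome, and analyses relating change to training time.

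**The concern.** The trial studies walking training. The 10MWT and WISCI II are its only dedicated tests of walking without the exoskeleton; the steps and walk time logged per session describe training in the device and have no counterpart in the control arm.

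The condition leaves out the people of most interest. A participant who cannot walk at enrolment and can at discharge has one value at most, so no change score and no place in a paired analysis. If the condition is judged again at discharge, the people tested there are selected on a state reached after randomisation that the intervention is meant to change. An arm that turns more non-walkers into walkers then adds more weak walkers to its own tested group, which pulls the visible difference toward zero.

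At stake is the usefulness of the two supporting walking measures. The loss cannot be repaired later if walking status at enrolment was not recorded.

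**Working it through.** The plan states no sample size, power or rate for these tests, so there is no figure of its own to reproduce. The check has two parts.

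**1. What each reading of the condition yields**

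- *Judged once, at enrolment.* Only baseline walkers are ever tested. Those who gain walking are never tested. The group is set by baseline status, not by response to treatment.
- *Judged at each visit, change scores analysed.* Both values are needed, so the group is those who walk at both visits. Those who gain walking are tested once and drop out of the analysis.
- *Judged at each visit, discharge values analysed.* Everyone walking at discharge enters, including those who gained walking. The group is selected after randomisation.

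No reading gives a change score to a participant who gains walking.

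**2. Illustration of size**

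From the documents: 20 intervention and 10 control participants (sections 6.1.1 and 6.2).

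Assumed, because the documents are silent: latent walking ability at baseline is standard normal; a person walks if above a threshold c set so that 10%, 20% or 30% walk at baseline; discharge ability = baseline + 0.8 + E × arm + noise with SD 0.6; E, the true effect, is 0.3, 0.5 or 0.8 baseline SD.

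Quantities:
- Discharge difference = mean ability of intervention walkers at discharge minus that of control walkers at discharge.
- Change difference = the same contrast in change, among those above c at both visits.
- Number with both values = 20 × P(both, intervention) + 10 × P(both, control).

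| Walk at baseline | True E | Walk at discharge, control / intervention | Discharge difference (share of E) | Change difference | Both values, intervention + control |
|---|---|---|---|---|---|
| 10% | 0.3 | 34% / 44% | 0.09 (30%) | 0.27 | 2.0 + 1.0 |
| 10% | 0.5 | 34% / 51% | 0.16 (32%) | 0.47 | 2.0 + 1.0 |
| 10% | 0.8 | 34% / 61% | 0.28 (35%) | 0.76 | 2.0 + 1.0 |
| 20% | 0.3 | 49% / 59% | 0.12 (40%) | 0.28 | 4.0 + 1.9 |
| 20% | 0.5 | 49% / 65% | 0.20 (40%) | 0.47 | 4.0 + 1.9 |
| 20% | 0.8 | 49% / 74% | 0.35 (44%) | 0.77 | 4.0 + 1.9 |
| 30% | 0.3 | 59% / 69% | 0.13 (43%) | 0.28 | 5.9 + 2.9 |
| 30% | 0.5 | 59% / 75% | 0.24 (48%) | 0.47 | 6.0 + 2.9 |
| 30% | 0.8 | 59% / 82% | 0.41 (51%) | 0.77 | 6.0 + 2.9 |

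Participants who gain walking and have no baseline value, for 20% and E = 0.5: they are 70% of tested intervention and 60% of tested control participants, so 20 × 0.65 × 0.70 + 10 × 0.49 × 0.60 = 9.1 + 2.9 = 12 of 30. Over the grid the count runs from about 9 to 14.

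The change difference keeps 90-96% of the true effect (0.27/0.3 to 0.77/0.8) but rests on about 3 to 9 people. The discharge difference keeps 30-51%.

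A second set of assumptions (c = 1.0, mean gain 1.0, SD of gain 0.8, E = 0.6) gives 16% walking at baseline, and 50% control and 68% intervention at discharge. About 4.7 of 30 have both values and about 14 gain walking. The change difference is 0.54 (0.54/0.60, about 90%) and the discharge difference 0.25 (0.25/0.60, about 42%). If the condition is judged at enrolment only, the change difference is 0.60, with no bias.

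**The case against.** The strongest reply is that the plan does not clearly specify any comparison of these tests between arms. They are not listed endpoints, and the change-score comparison is written for hypotheses on ISNCSCI/FIM/SCIM, pain and CRP. This stands, and it confines the point to supporting measures. It does not remove the point: both tests sit under efficacy assessments at two visits, and the reference to each outcome can be read to include them.

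Three stronger readings are tempting, and the documents do not support them.

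- A reader might infer that every comparison between arms would be conditioned on a result of treatment. That holds only for discharge values among people who qualified at discharge. A change score in those tested at both visits is nearly unbiased in the illustration, and a condition judged at enrolment selects on baseline status. One reservation: section 8.1 places the first test after enrolment without saying whether it precedes randomisation.
- A reader might infer that the result could turn against the exoskeleton arm. In every scenario the difference shrinks but stays positive.
- A reader might infer that the condition contradicts the purpose of WISCI II, which grades assistance and devices. Because the term is undefined, and the 10MWT is specified as done without the exoskeleton, walking independently could mean without the device but with aids or help. This is a tension, not a proven contradiction.

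It is also fair to say that latent ability in SD units is neither a WISCI II rank nor a 10MWT time, so the sizes are only illustrative.

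**Conclusion.** The point holds, with limited reach. Followed as written, section 8.1 leaves anyone who gains walking during the stay without a change score on either test, and it does not settle who is tested or when. That conclusion needs no assumption beyond the text of sections 5.1, 8.1 and 9.2.1.

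The size rests on assumed inputs. For 10-30% walking at baseline and true effects of 0.3-0.8 SD, a change-score comparison is close to unbiased but uses a handful of people, while a comparison of discharge values among walkers loses roughly half to two-thirds of the effect. The three main hypotheses and the FIM-based sample size are not affected. The change is worth making because it costs little and cannot be made after the data are in.

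**What to change.** In section 8.1, remove the condition as a rule for who receives a score. At enrolment and at discharge:

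- give every participant a WISCI II rating, with the lowest rank if unable to walk 10 m;
- record the 10MWT as speed, with 0 m/s if unable; no attempt is needed to enter that value;
- if walking independently is kept as a descriptive status, define it and record it for everyone at both visits.

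In section 9.2.1, state that any comparison of these supporting measures between arms uses a rank method in all randomised participants with assessments. Mann-Whitney is already in the plan. The tests need not become listed endpoints.

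The cost is a short protocol edit, a brief rating for non-walkers, and ties at the lowest value. If everyone not walking independently at discharge took that value, the ties would number 20 × 0.35 + 10 × 0.51 = 12.1 of 30 for 20% walking at baseline and E = 0.5. Over the grid this runs from about 8 to 18, and there would be more at enrolment. Ties on WISCI II should be fewer, because it also grades assisted walking. Ties reduce power, but these participants are now in the comparison instead of missing from it.

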8.2 SAFETY AND OTHER ASSESSMENTS

Once the study attending physicians ([name]) and rehabilitation clinicians identify potential subjects for the study, they will introduce the study to them and ask their permission for referring them to the study team. If they express interest, the study team will approach subjects and provide more detailed information about the study to them. If participants agree, the informed consent process will be proceeded.

Once the consent form is signed, research team members and the study physicians ([name]) will begin the screening process using the study's inclusion/exclusion criteria. Medical record review will also be conducted to identify any other medical concerns that might increase the risks associated with participation.

8.3 ADVERSE EVENTS AND SERIOUS ADVERSE EVENTS

8.3.1 DEFINITION OF ADVERSE EVENTS (AE)

There are several potential risks associated with the EAW and the testing procedures.

- 1) EAW training has the potential risks of falls resulting in bone fracture, muscle soreness, joint damage, or other musculoskeletal injury, and/or autonomic dysreflexia (AD).
- 2) Persons using the Ekso may also be at risk for bruising, skin abrasion, pressure sores, soft tissue injury, or adverse tissue reaction from direct contact of the body with the device. Notable contact points exist between the sacrum and back pack, hip pads and greater trochanters, shin pads and shins, and with the straps for the thighs and legs.
- 3) Lastly, the device itself could malfunction due to premature battery failure, interference with other electrical equipment or devices, electrical shock, or unanticipated operation (stoppage or unintended movement).

8.3.2 DEFINITION OF SERIOUS ADVERSE EVENTS (SAE)

A Serious Adverse Event (SAE) is defined by the ICH for Clinical Safety Data Management and CSP Global SOP 3.6.2, as any untoward medical occurrence that: results in death, is life threatening, requires inpatient hospitalization or prolongation of existing hospitalization, results in persistent or significant disability or incapacity, a congenital anomaly/birth defect, or any other condition that, based upon medical judgment, may jeopardize the subject and require medical, surgical, behavioral, social or other intervention to prevent such an outcome.

8.3.3 ADVERSE EVENT REPORTING

In this study, all AEs will be collected by the Sponsor. The reporting period for AEs begins when the participant signs the informed consent form and continues until the participant's completion or early termination of participation or the end of the study.

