8.3.4 SERIOUS ADVERSE EVENT REPORTING

All AEs and SAEs that occur throughout the study, whether study-related or non-related, will be documented and reported to the IRB, as per IRB regulations. AE/SAE report forms will be completed within 48 hours throughout the study for each participant. We will keep a running log of all AE/SAEs (anticipated and unanticipated) throughout the study. Any SAE will be reported to the IRB within 24 hours, and the study will be suspended until the study physician states that it is safe to resume the study.

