9 STATISTICAL CONSIDERATIONS

9.1 SAMPLE SIZE DETERMINATION

All statistical tests will be 2-sided. The outcome measures will be tested at a 0.05 level of significance. SPSS will be used to conduct the statistical analyses. All participants who have EAW sessions will be included (regardless of the number of sessions they complete before discharge, but the number and reason of missing EAW sessions will be recorded). To test the three main hypotheses of the proposed study, the change score of each outcome between baseline and discharge will be calculated. The change score will be compared between the intervention and control groups using independent t-test analyses (if the outcomes are not normally distributed, Mann-Whitney tests will be used).

Since the primary aim of the study is to compare the improvement of FIM scores between the groups, the FIM score results from the preliminary data were used to perform the power analysis for this study. In the preliminary data, the mean change in FIM score from the intervention group was 35 ± 12 , and the control group was 22 ± 13 . The effect size of the FIM score change in our preliminary data was 1.07 (controlling for the different number of participants between the two groups). The power analysis showed that using the effect size (1.07) and 0.05 level of significance with two-sided analysis in independent t-test, a total of 30 participants will provide the study 80% power.

To account for an expected attrition rate of about 25%, 40 participants will be enrolled. It is expected that 30 participants will complete the study (the reasons and number of screening failures and dropouts will be recorded).

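### AE reporting ends when staff withdraw an EAW participant over a safety concern, and the two reporting sections disagree on an AE that turns serious afterwards

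*Combined protocol and SAP*

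**What the plan says.** - **End of the AE period (8.3.3).** Reporting starts at consent and continues to the participant's "completion or early termination of participation or the end of the study".
- **Withdrawal by staff (7.1).** "Subjects may be withdrawn without their consent" on two grounds. One is that they prove ineligible. The other applies "if during an exoskeleton instruction session, research staff or clinicians have concerns about" how well or how safely someone is performing. A further condition is that staff "feel that discontinuing involvement would be in the best interest of the participant". Section 6.1.1 gives the control arm no EAW, so the second ground can arise only in the intervention arm.
- **After withdrawal (7.2, 7.3).** Section 7.2 asks nothing further of participants who leave early, and 7.3 is marked not applicable. On data, 7.2 adds: "Their health information may still be used or shared after their withdraw their authorization if they have an adverse event" from taking part.
- **SAE definition (8.3.2).** The criteria include an event that "requires inpatient hospitalization or prolongation of existing hospitalization".
- **SAE reporting (8.3.4).** AEs and SAEs over the course of the study are to be documented and reported, with no cut-off for an individual participant. "Any SAE will be reported to the IRB within 24 hours, and the study will be suspended" until the study physician says it may resume.
- **Attrition (9.1).** "To account for an expected attrition rate of about 25%, 40 participants will be enrolled". Reasons for dropout are recorded.

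**The concern.** Each rule is unremarkable alone; the difficulty is in how they combine. A participant about whom staff have a safety concern can be withdrawn by staff while still an inpatient, and under 8.3.3 the AE period then closes. The usual reason to stop collecting data at withdrawal is respect for the participant's choice to leave, and it does not apply when staff make the decision.

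The timing matters because everyone in this trial is already in hospital. Whether an injury prolongs the stay may become clear only late in that stay. Suppose a skin injury at a device contact point, a risk listed in 2.3.1, is logged and the participant is withdrawn. The sore then worsens and delays discharge. The SAE criterion is met only after early termination, and the plan does not say clearly whether the expedited report and the suspension then follow.

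At stake are the completeness of the AE record, reporting to the IRB and the suspension rule, which acts on a single SAE. Sections 2.1 and 2.2 name safety among the things the trial is meant to determine. No test of safety is planned, so no p-value or power figure is involved.

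**Working it through.** **1. What the text covers, case by case.** The participant is an EAW participant withdrawn under the second ground in 7.1.

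| Event | 8.3.3 | 8.3.4 | Result |
|---|---|---|---|
| Event that prompts the withdrawal | Inside the period | Covered | Logged and reported |
| Event serious at once, before withdrawal | Inside | Covered | 24-hour report and suspension apply |
| New non-serious AE after withdrawal, before discharge | Outside | Covered only if the general wording overrides 8.3.3 | Outside the stated AE period |
| Logged AE that becomes serious after withdrawal | Period closed | No participant-level cut-off | The two sections conflict |

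For the third row, 8.3.3 is the specific rule on when AE reporting stops. It lists early termination as an endpoint alongside the end of the study. If AE reporting ran to the end of the study for everyone, naming early termination would have no effect. The permission in 7.2 allows health information to be used; it does not require anyone to collect it and does not lengthen the period.

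**2. Ceiling on the number of people.** Inputs from 9.1 and 6.2: 30 completers, 25% attrition, allocation 20:10.

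- Plan's own figure: 30 / (1 − 0.25) = 40 enrolled, which reproduces.
- Expected attrition: 0.25 × 40 = 10.
- Assuming enrolment at 2:1: 40 × 2/3 = 26.7 EAW and 13.3 control.
- Assuming the same attrition in each arm: 0.25 × 26.7 = 6.7 EAW and 0.25 × 13.3 = 3.3 control.

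So about 7 in the EAW arm is a ceiling for all reasons together. Some may be screening failures, and the documents do not say how many would leave over a safety concern.

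**3. Does this tilt the comparison of arms?** Observation time lost in an arm is a × (1 − t), where a is the share withdrawn and t the share of the stay already elapsed. With a = 0.25 and t = 0.5 (assumed), the loss is 0.25 × 0.5 = 12.5% in the EAW arm and 12.5% in the control arm, a difference of zero. A difference appears only if withdrawals are unequal between arms, and the documents give no basis for a figure.

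**4. Illustration only.** Let w be the number of EAW participants withdrawn over safety, and q the chance that each has a new AE or an upgrade to serious before discharge. The chance of at least one such event is 1 − (1 − q)^w.

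| w | q = 10% | q = 25% | q = 50% |
|---|---|---|---|
| 0 | 0% | 0% | 0% |
| 1 | 10% | 25% | 50% |
| 2 | 19% | 44% | 75% |
| 7 | 52% | 87% | 99% |

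Both w and q are assumptions. The w = 7 row would need every expected EAW dropout to be a safety withdrawal, and q pools new AEs with upgrades. The range from 0% to 99% shows only that the size cannot be known from the documents.

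**The case against.** Two stronger readings are tempting, and neither is supported.

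*A late SAE is exempt from the 24-hour report and the suspension.* A reader might infer this from 8.3.3. But SAEs have their own section, 8.3.4, which spans the study, keeps a running log and sets no cut-off for an individual participant. Nothing in 8.3.3 says that an event already logged stops being updated. Section 8.3.4 also defers to IRB regulations, which are not in the documents and may settle the matter. The text supports a conflict, not an exemption.

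*The rule makes EAW look safer.* One ground for closing the window exists only in the EAW arm, so this is an easy inference. But ineligibility and voluntary withdrawal close the window in both arms, equal attrition removes the difference, and EAW sessions bring closer observation that may raise AE counts in that arm. The plan also includes no comparison of AEs by arm.

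The remaining defence is that stopping EAW need not mean leaving the study. Section 7.1 is headed as discontinuation of the intervention and is permissive. Section 6.1.1 lets the clinical team adapt the sessions, and 9.1 and 9.2.1 keep everyone who had EAW sessions in the analysis however few they completed. That has force, but the body of 7.1 speaks of withdrawing the subject and of ending involvement, so the ambiguity stands.

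It is also fair that this is a single inpatient site with its own study attending physicians, and that 5.2 excludes people with skin problems at contact areas. A serious late injury would probably be seen. That lowers the practical risk but does not make reporting it to the study a requirement.

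**Conclusion.** The point holds as a minor one. On the stated rules, a new AE after a staff withdrawal over safety, but before AIR discharge, lies outside the AE reporting period. For a logged AE that later becomes serious, the plan gives two answers. This rests on reading withdrawal under 7.1 as early termination of participation, which its wording supports although its heading points the other way.

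The size is unknown. It is zero if nobody is withdrawn over safety, and at most about 7 EAW participants if all expected EAW attrition were of this kind and fell in proportion to allocation. The consequence is confined to the safety record and the operation of the reporting and suspension rules.

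**What to change.** 1. In 8.3.3, run the AE and SAE period from consent to AIR discharge for every randomized participant, including those withdrawn by staff. Use chart review after withdrawal. Where a participant withdraws authorization in writing, stay within what 7.2 permits.
2. Follow open AEs to discharge and re-grade each against 8.3.2 at that time, including whether it prolonged the stay. Make 8.3.4 refer to the same period, so that the 24-hour report and the suspension have one rule.
3. In 7.1, state that stopping EAW for safety does not by itself end participation in the study.

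The cost is a short amendment, matching consent wording, and chart review for at most about 10 of 40 participants. No visits or tests are added.
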